#### 7.10 Electrocardiogram

For all subjects assigned to the MC2-01 cream, a 12-lead ECG will be recorded at Visit 1/Day 0, Week 4 and Week 8 visits. Recording will take place after 5 minutes' rest in supine position.

Recordings will be promptly transmitted to the central ECG vendor for interpretation. Additional (unscheduled) ECGs can be recorded for safety reasons at any time based on the judgment of the investigator.

Clinically significant findings will be reported as medical history if detected at Visit 1/Day 0. At subsequent visits, any new clinically significant finding will be reported as an AE. Any ECG abnormalities will be carefully monitored and if necessary the subject will be withdrawn from the trial.

## 7.11 The Psoriasis Treatment Convenience Scale

The Psoriasis Treatment Convenience Scale must be completed by the subjects before any other assessments are performed. The PRO assessments are to be performed as specified in the visit schedule (see [Table 7-2](#), and [Table 7-3](#)).

The aim of the Psoriasis Treatment Convenience Scale is to assess the impact and convenience of psoriasis treatment. The scale has been tested for content validity through focus group interview with 20 patients and adapted based on the responses. The scale consists of 5 disease-specific, self-report questions with a recall period of 1 week and rated on a 1-10 scale.

1. How easy was the treatment to apply to the skin?
2. How greasy was the treatment when applying it to the skin?
3. How moisturised did your skin feel after applying the treatment?
4. How much did treating your skin disrupt your daily routine?
5. Overall, how satisfied were you with the medical treatment?

## 7.12 Investigator Assessments

The investigator assessments are to be performed by a dermatologist, a physician with at least 1 year of experience in dermatology, or a Nurse Practitioner or Physician Assistant with at least 2 years of experience in dermatology. For physicians, Nurse Practitioners and Physician Assistants who do not fulfill the requirement regarding dermatological experience, the person must be preapproved by the sponsor. The assessments are to be performed as specified in the visit schedule [Table 7-1](#), [Table 7-2](#) and [Table 7-3](#).

### 7.12.1 Physician's global assessment of psoriasis severity

The Physician's Global Assessment (PGA) measures the investigator's or designee's impression of the disease at a single point using a defined, 5-point, static PGA scale (clear, almost clear, mild, moderate or severe); see [Table 7-5](#). The PGA assessment will represent the *average* lesion severity on scalp, trunk and limbs (excluding face, genitals, and intertriginous areas). The assessments will be based on the condition of the disease at the time of evaluation, and not in relation to the condition at a previous visit.

**Table 7-5 Physician's Global Assessment (PGA)**

Score	Grade	Definition
0	Clear	Plaque thickening = no elevation or thickening of normal skin Scaling = no evidence of scaling Erythema = none (no residual red colouration but post-inflammatory hypo or hyperpigmentation may be present)
1	Almost clear	Plaque thickening = none or possible thickening but difficult to ascertain whether there is a slight elevation above normal skin level Scaling = none or residual surface dryness and scaling Erythema = light pink colouration
2	Mild	Plaque thickening = slight but definite elevation Scaling = fine thin scales partially or mostly covering lesions Erythema = light red colouration
3	Moderate	Plaque thickening = moderate elevation with rounded or sloped edges Scaling = coarse scale layer at least partially covering most lesions Erythema = definite red colouration
4	Severe	Plaque thickening = marked or very marked elevation typically with hard or sharp edges Scaling = non-tenacious or thick tenacious scale predominates, covering most or all of the lesions Erythema = very bright red colouration, extreme red coloration or deep red coloration

### 7.12.2 Body surface area involvement of psoriasis vulgaris

The investigator or designee will assess the extent of the subject's psoriatic involvement on the scalp, trunk and limbs (excluding face, genitals, and intertriginous areas).

The total psoriatic involvement on the scalp, trunk and limbs will be recorded as a percentage of the total BSA, estimating that the surface of the subject's full, flat palm (including the five digits) correlates to approximately 1% of the total BSA. If the subject has psoriasis of guttatae character, these elements will be part of the estimation of total psoriatic involvement. The purpose of this is to obtain an estimate of the area on the trunk and limbs to be treated with trial medication.

### 7.12.3 Local skin reactions

The local skin reaction assessment involves signs assessed by the investigator or designee and symptom reported by the subject.

The investigator will assess the treatment area and/or immediate surrounding for the following identified signs:

- Perilesional erythema, scaling, edema, atrophy, vesicles and erosion/ulceration;
- Lesional vesicles, and erosion/ulceration.

The intensity of each local skin reaction category is to be graded according to the scale in [Table 7-6](#). The most severe intensity observed for each category of the local skin reaction assessment is to be recorded.

The subject will assess burning and pain after application. The investigator or designee will explain the scores in [Table 7-6](#) and the subject will tell which one to mark.

Signs and symptoms fulfilling the adverse advent definition should be reported as adverse events.

**Table 7-6 Local Skin Reaction Scores**

Investigator assessment of the lesional area				
	0 (absent)	1 (Mild)	2 (Moderate)	3 (Severe)
Erosion/ulceration in lesional area	None	Barely visible erosion	Distinct erosion	Ulceration
Vesicles in lesional area	None	Barely visible vesicles	Distinct vesicles	Bullae
Investigator assessment of the perilesional area				
	0=absent	1 (Mild)	2 (Moderate)	3 (Severe)
Erythema in perilesional area	None	Barely visible erythema	Distinct erythema	Dark red erythema
Scaling in the perilesional area	None	Barely visible scaling	Distinct scaling	Gross scales
Edema in perilesional area	None	barely palpable swelling	Easily palpable swelling	Gross swelling
Atrophy in perilesional area	None	Barely visible thinning	Distinct thinning	Striae
Vesicles in perilesional area	None	Barely visible vesicles	Distinct vesicles	Bullae
Erosion/ulceration in perilesional area	None	Barely visible erosion	Distinct erosion	Ulceration
Subject Assessment				
	0 (absent)	1 (Mild)	2 (Moderate)	3 (Severe)
Burning or pain after application	None	Barely present and disappears within few minutes	Distinct and lasts for up to an hour	Pronounced and lasts for several hours

## 7.13 Adverse Events

### 7.13.1 Adverse events assessments

The investigator or designee is responsible for obtaining, assessing, and documenting all AEs during the study. Adverse Events information will be collected from the time of the signature of the informed consent form and first trial-related activity performed until the end of the study. An

AE is an untoward medical occurrence in any subject during the trial which does not necessarily have a causal relationship with the trial drug treatment.

All AEs will be documented in the eCRF, including a description of each AE, AE relationship to trial product administration, start and stop dates, seriousness, severity, action taken and outcome.

Any AE that meet the serious criteria must be reported on the eCRF and on a separate SAEs report form. SAEs must be reported to the United BioSource Corporation (UBC) within 24 hours of awareness.

Throughout the trial, the occurrence of AEs should be sought by nondirective questioning of the subject at each visit during the trial. Information on AEs can also be obtained from signs and symptoms detected during examination, observations made by the trial site personnel, or spontaneous reports from subjects. Pre-existing conditions that worsen during the trial should also be recorded as AEs.

AEs requiring therapy must be treated with recognised standards of medical care to protect the health and well-being of the subject. Treatment due to an AE will be recorded in the subject's records and on the appropriate eCRF.

Any AE that is considered related to the trial product must be followed by the investigator until it is resolved or until the medical condition of the subject is stable; all relevant follow-up information will be reported to the MC2 or designee.

The outcome of an AE will be classified as recovered, recovered with sequelae, recovering/resolving, ongoing, or death.

### **7.13.2 Timing**

AEs will be collected/assessed during the period from the time of the signature of the informed consent form by the subject and first trial-related activity performed.

### **7.13.3 Severity of adverse events**

The investigator is to classify the severity (intensity) of an AE according to the following definitions:

- Mild – The subject was aware of the signs and symptoms but the signs and symptoms were easily tolerated and does not interfere with daily activity.
- Moderate – The signs and symptoms were sufficient to restrict, but did not prevent, usual daily activity for the subject. The subject is still able to function.
- Severe – The subject was unable to perform usual daily activity.

The maximum intensity of an AE (mild, moderate, or severe) will be assessed taking into account the possible range of intensity of the symptom(s).

#### **7.13.4 Relationship of an adverse event to trial treatment**

The investigator is responsible to assess the relationship of an AE to the IP using good clinical judgment and the following definitions:

Not Related	The AE is clearly explained by another cause not related to the trial product administration; the temporal relationship of the AE to IP administration makes a causal relationship unlikely, or, concomitant medication, therapeutics interventions, or underlying condition provide a sufficient explanation for the observed AE
Possibly Related	The AE and administration of trial product are temporally related, but the AE can be explained equally well by causes other than the trial product administration
Probably Related	The AE and use of trial product are temporally related, and the AE is more likely explained by trial product administration than by other causes
Definitely Related	The AE and trial product administration are related in time, and a direct association can be demonstrated. Concomitant medication, therapeutics interventions, or underlying conditions do not provide a sufficient explanation for the observed AE

#### **7.13.5 Unexpected adverse events**

Any AE assessed as related to the IP will be assessed for expectedness by the sponsor or designee. An AE is considered “unexpected” if its nature or severity is not consistent with information in the MC2-01 Investigator’s Brochure (for MC2-01 cream) or Tacalonex® Ointment prescribing information (for active comparator).

“Unexpected” as used in this definition, also refers to AEs that are mentioned in the Investigator’s Brochure or product prescribing information as occurring with a class of drugs or as anticipated from the pharmacological properties of the drug, but are not specifically mentioned as occurring with the particular drug under investigation.

### 7.13.6 Trial medication overdose

An overdose of the investigational product, i.e., a dose that is higher than the highest dose under clinical investigation or the known therapeutic dose, will be fully documented even if no toxic effects were observed and will be considered an AE.

The maximum weekly dose of the MC2-01 cream and the comparator is 100 g. The treated area should not be >30% of the body surface area.

Use above the recommended dose may cause elevated serum calcium, which should rapidly subside when treatment is discontinued. Excessive prolonged use of topical corticosteroids may suppress the pituitary-adrenal functions, resulting in secondary adrenal insufficiency that is usually reversible. In such cases, symptomatic treatment is indicated.

### 7.13.7 Pregnancy

Any pregnancy occurring from date of the Informed Consent signature until study completion must be reported immediately to the MC2 or designee as soon as it becomes known to the investigator and not later than within 24 hours of his/her knowledge of the occurrence of the pregnancy (see [Section 13.2](#)).

Investigator must actively follow-up, document and report to MC2 or designee the progress of the pregnancy until outcome is reached.

### 7.13.8 Serious adverse event

An SAE is any untoward medical occurrence that at any dose:

- Results in death
- Is life-threatening
- Requires in-patient hospitalisation or prolongation of existing hospitalisation
- Results in persistent or significant disability/incapacity
- Is a congenital anomaly/birth defect, or is an important medical event
- Other serious or important medical event

The death of a subject enrolled in a trial is per se not an event, but an outcome. Any event resulting in a fatal outcome must be fully documented and reported, regardless of the causality relationship to the IP.

Any medical important events that may not result in death, be life-threatening, or require hospitalisation may be considered an SAE when, based on appropriate medical judgment, they may jeopardise the subject or the subject may require medical or surgical intervention to prevent one of the outcomes listed in the above definitions.

Any pre-planned hospitalisations that are known at the time of signing the ICF will not be recorded as SAEs, however they will be recorded as AEs only.

Any SAE, whether or not deemed drug-related or expected, must be reported immediately to the MC2 or designee as soon as it becomes known to the investigator and not later than within 24 hours of his/her knowledge of the occurrence of an SAE (see [Section 13.2](#)). The investigator will document such events in the best possible detail on the SAE Report Form.

A suspected unexpected serious adverse reaction (SUSAR) is an SAE that is both unexpected (not consistent with the current Investigator's Brochure or Tacalonex® Ointment prescribing information,, and for which there is evidence to suggest a causal relationship between the drug and the SAE. The Institutional Review Board (IRB)/Independent Ethics Committee (IEC) will be informed of SUSARS according to local requirements. All investigators participating in the trial will also be notified of unexpected SAEs. The sponsor will report SAEs and other events requiring expedited reporting to regulatory authorities as required.

Investigator instructions for reporting SAEs are provided in [Section 13.2](#).

#### **7.14 Unscheduled Visit**

An unscheduled visit may be performed at any time during the trial if judged necessary by the Investigator, such as for a severe reaction, suspected pregnancy, clinically significant AE, or clinically significant local skin reaction result. Details of the event are to be recorded in the subject's records.

#### **7.15 Follow-up Visit**

A follow-up visit is required for the following reasons:

- Unresolved related AEs.

For subjects assigned to the MC2-01 cream:

- If the albumin-corrected serum calcium was above the normal reference range at Week 4 and Week 8 a repeat should be done 14 days ( $\pm$  2 days) after.
- If the HPA axis suppression is noted at Week 8 an ACTH challenge test should be performed 28 days ( $\pm$  2 days) after.

#### **7.16 Early Termination**

If a subject withdraws from the trial prior to Week 4 and for subjects assigned to the MC2-01 cream prior to Week 8, the subject is to return to the site for an unscheduled visit. The following procedures should be performed:

- Collect all trial materials from the subject.

- Assess compliance
- Review any concomitant medication used since the previous trial visit.
- Record any AEs.
- Physical examination and vital signs
- Perform a UPT for females of childbearing potential.
- ECG (only for subjects assigned to the MC2-01 cream)
- Haematology, biochemistry, and urinalysis.
- PGA
- BSA
- Psoriasis Treatment Convenience Scale (Only if before Week 4)

## **8.0 STATISTICAL METHODS AND DETERMINATION OF SAMPLE SIZE STATISTICAL AND ANALYTICAL PLANS**

### **8.1 General Considerations for Data Analysis**

The methodology presented below represents a brief overview of the statistical methods that will be fully detailed in the statistical analysis plan (SAP). The SAP will be finalised before the database is locked. Any changes to the methods described in the final SAP will be described and justified in the clinical trial report. All statistical analyses will be performed using SAS statistical software (Version 9.2 or higher).

It is planned that the data from all centres that participate in this protocol will be combined so that an adequate number of subjects will be available for analysis. No imputation will be made for missing data.

### **8.2 Sample Size and Power Considerations**

The choice of sample size in this trial is not based on statistical considerations, but rather on regulatory considerations with respect to common practice in maximum use studies evaluating pharmacokinetic profiles and evidence of HPA safety. The chosen number of approximately 25 subjects included in the PK population at Week 4 in each treatment arm is considered sufficient to compare the PK properties corresponding to the two treatments.

### **8.3 Analysis Populations**

The analysis populations are defined as follows:

- **PK population:** all subjects in the Safety population who have received the planned application of treatment at the Week 4 or Week 8 visit, respectively, and have had at least one post-application blood draw for PK assessment at the corresponding visit.

- **Safety population:** all subjects who are randomized and have been dispensed the trial medication at Randomisation/Day 0, excluding subjects who return all of the trial medication unopened. The Safety population will be used for all safety analyses other than evaluation of the HPA-axis.
- **HPA population:** all subjects in the Safety population that are assigned to MC2-01 cream and who show normal HPA function at Baseline. Since the objective of the analysis is to estimate the risk to subjects with normal HPA function of HPA-axis suppression following treatment, subjects who meet the definition of HPA-axis suppression at Baseline will be excluded from the analysis. The HPA population will be used for the HPA axis suppression analysis.

#### **8.4 Background and Demographic Characteristics**

Descriptive statistics will be used to summarise demographic characteristics (age, sex, and race) and background characteristics for the Safety population. Past/coexistent medical history information, physical examination observations, and vital signs information for all randomised subjects will be presented in a by-subject listing.

#### **8.5 Trial Medication/Exposure**

Descriptive statistics will be used to summarise trial medication exposure for the Safety population. Measures of trial medication exposure will include the total duration of treatment, the total weight of trial medication used, and the total number of applications.

#### **8.6 Prior and Concomitant Therapy**

Prior and concomitant medication information for all randomised subjects will be presented in a by-subject listing.

#### **8.7 Analysis of Pharmacokinetics**

All available concentration results will be summarised using appropriate descriptive statistics for active ingredients (BDP and CAL) and for their major metabolites. Median and individual concentration versus time curves will be plotted (linear and semi-log plots).

Plasma PK parameters ( $AUC_{0-t}$ ,  $AUC_{0-\infty}$ ,  $AUC_{0-7}$ ,  $C_{max}$ ,  $T_{max}$ , and  $T_{1/2}$ ) will be calculated at Week 4 and Week 8 (subjects randomised to MC2-01 cream only). The PK parameters  $AUC_{0-7}$  and  $C_{max}$  will be calculated using standard formulas inserting the lower limit of quantification for non-quantifiable levels of the analyte; therefore,  $AUC_{0-7}$  will be an upper limit in case at least one time point shows a non-quantifiable level of the analyte, and  $C_{max}$  will be an upper limit in case all time points show non-quantifiable levels of the analyte. For a given analyte, the PK parameters  $AUC_{0-t}$ ,  $AUC_{0-\infty}$ ,  $T_{max}$ , and  $T_{1/2}$  will be calculated if data allow. The PK parameters will be summarised using appropriate descriptive statistics including median, lower and upper quartiles, minimum and maximum.

### **Assessment of systemic exposure (Week 4)**

Assessment of relative systemic exposure in the two treatment arms will be performed for AUC0-7 and Cmax at Week 4. It will be based on an analysis of variance for censored data for each parameter, assuming a log-normal distribution of the PK parameter. Geometric mean ratio and associated 90% confidence interval will be presented.

### **8.8 Analysis of Safety**

The assessment of HPA axis suppression (using pre- and post-stimulation cortisol levels) and of changes in calcium metabolism are the primary safety endpoints in this trial.

Other assessments of safety will be based mainly on the frequency of AEs and on the number of laboratory values that fall outside of predetermined ranges, presented for the two periods, Weeks 1 to 4 and Weeks 5 to 8, separately. Adverse events will be presented in data listings and summarized by frequency and severity for each treatment group for each period. Laboratory and vital sign data will be presented in data listings. Abnormal laboratory findings will be presented. The analysis of safety will be described in the SAP.

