Trial Design:	
This is a Phase 2, randomised, open-label, parallel-group, multicentre trial in which the investigational product, MC2-01 cream, and calcipotriene/betamethasone ointment (comparator) is investigated in subjects with clinically diagnosed extensive psoriasis vulgaris.
 
After having provided informed consent, the subjects will undergo screening procedure. Subjects that fulfil the inclusion and exclusion criteria are randomly assigned in a 1:1 ratio to receive the MC2-01 cream or the comparator.
 
Subjects assigned to the MC2-01 cream will be treated once-daily for 8 weeks and the subjects assigned to the comparator will be treated once-daily for 4 weeks.
 
At Week 4, the pharmacokinetic (PK) profile of calcipotriene (CAL), betamethasone dipropionate (BDP) and their main metabolites MC1080 and betamethasone 17-propionate, respectively, will be assessed for both treatment groups. At Week 8, the PK profile of calcipotriene, betamethasone and their main metabolites will be assessed for the MC2-01 cream treatment group only.
 
The effect of use of MC2-01 cream on the hypothalamus-pituitary-adrenal (HPA) axis and calcium metabolism will be evaluated at week 4 and week 8.
 
The maximum trial duration for each subject will be approximately 12 or 16 weeks and includes a screening period of up to 4 weeks (if washout of medication is required), a treatment period of 4 or 8 weeks, and a follow-up period of up to 4 weeks (if required for follow-up of adverse events, calcium concentrations, and/or HPA axis suppression).

Sample Size:	
It is planned to enrol approximately 60 subjects with the aim to have 25 subjects included in the PK population after 4 weeks of treatment in each treatment arm.
 
The choice of sample size in this trial is not based on statistical considerations, but rather on regulatory considerations with respect to common practice in maximum use studies evaluating pharmacokinetic profiles and evidence of HPA safety

Trial Population:	Generally healthy males or non-pregnant females, at least 18 years of age, with a clinical diagnosis of plaque psoriasis (psoriasis vulgaris) of at least 6 months duration, with a Physician Global Assessment (PGA) of disease severity of at least moderate on the trunk, limbs and/or scalp and a treatment area between 20% and 30% of the BSA, excluding psoriatic lesions on the face, genitals, and intertriginous areas.

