## 2.2 Rationale of the Trial

To increase the likelihood that adequate quantifiable systemic concentrations of CAL and BDP and their main metabolites under maximal use conditions to determine the pharmacokinetic parameters in sufficient numbers of patients, *Taclonex® Ointment* has been selected as the comparator. MC2-01 cream will be compared to *Taclonex® Ointment* following once daily topical application under maximal use conditions in subjects with extensive psoriasis on the scalp, trunk, and limbs. Dosages will be up to 100 g per week for 8 weeks for MC2-01 cream and for 4 weeks for *Taclonex® Ointment*.

At Week 4, blood samples will be taken at selected intervals after topical dosing of each trial medication. Upper limits will be calculated for the PK parameters, area under the concentration-time curve (AUC) from time zero to the planned last PK blood sampling time point of 7 hours (AUC0-7) and maximum plasma drug concentration (Cmax). To the extent the data allow to calculate the PK parameters, the following parameters will be calculated: AUC from time zero to the last quantifiable concentration (AUC0-t), AUC from time zero to infinity (AUC0-∞), time to maximum plasma drug concentration (Tmax), and elimination half-life (T1/2).

*Taclonex® Ointment* is only approved for daily application for up to 4 weeks, whereas it is the intention that MC2-01 cream will be used daily for up to 8 weeks. The pharmacokinetic comparison between the two trial medications will be done at Week 4. Additional pharmacokinetic data at Week 8 will be obtained only from subjects receiving the MC2-01 cream.

Since MC2-01 cream is a combination of CAL and BDP, disturbance of calcium metabolism and adrenal function respectively could theoretically be the result if these two components are absorbed through the skin.

As the current trial is a MUS-T trial only subjects with upper level of disease involvement will be included. Inclusion criteria will be subjects with extensive psoriasis covering between 20-30% of the BSA on trunk, limbs and/or scalp. The intent of the inclusion criteria is both to take into account the potential risk that patients may decide to apply MC2-01 cream on the scalp and also to take into account precedent from previous approved CAL/BPD products.

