#### **8.8.3 Adverse events**

Adverse events will be coded using Medical Dictionary for Regulatory Activities (MedDRA) terminology. Treatment-emergent adverse events will be summarized by the overall incidence of at least one event, incidence by body system, and incidence by body system and preferred term. Each subject will contribute only once (e.g., the first occurrence) to each of the rates, regardless of the number of occurrences (events) the subject experiences. Treatment-emergent AEs will be summarised by severity (mild, moderate, or severe), and by relationship to trial product (none, unlikely, possible, probable, or definite). An adverse event is treatment-emergent if its date of onset is Day 1 (Baseline) or later.

Discontinuations from the trial due to AEs and SAEs will be listed by subject.

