#### **10.8.2.3 Adverse Events**

AE terms will be coded using MedDRA dictionary (version 20.0). A treatment-emergent AE (TEAE) is defined as an AE with a start date on or after the first application to trial medication (Day 1). If relationship to study medication is missing, the event will be conservatively summarized as being related to study drug. If intensity is missing, a separate category of missing intensity will be included in the summary table, and no imputation of severity will be performed. Through the data cleaning process, all attempts will be made to avoid missing values for relationship and severity.

All AEs will be presented in a by-subject listing, detailing the verbatim term given by the investigator, the PT, SOC, whether or not related to Cosyntropin or study procedure, location of AE to treatment area, start date, stop date, intensity, outcome, relationship to study medication (definitely, probably, possibly, and not related), action taken with study medication, action taken to treat the AE, seriousness and criteria for seriousness. For subjects assigned to MC2-01 cream, all TEAEs will be assigned to the Week 1-4 (starting from Day 1 to 28) or post-Week 4 period (starting from Day 29 and after) based on onset dates. Serious AEs and AEs leading to study drug discontinuation will be presented in a separate listing.

An overall summary of AEs will be presented by treatment and by period (MC2-01 group only). The summary will include the total number of events, frequency counts and percentages with:

- Any AE
- Any TEAE
- Any serious TEAE
- Any treatment-related TEAE
- Any TEAE leading to study drug discontinuation

Summaries of the incidence of TEAEs will be displayed by treatment and by period (MC2-01 group only) according to the following:

- All TEAEs by PT in descending order of frequency (the combined frequency of both treatments)
- All TEAEs by SOC, PT, and maximum severity (mild, moderate, or severe)
- All TEAEs by SOC, PT, and maximum relationship (recorded as 'definitely', 'probably', and 'possibly') to the study drug

At each level of summarization, a subject will be counted once if he/she reported one or more events. The severity of TEAEs and relationship to study drug will be summarized in a similar manner. For summaries of relationship to study drug, a subject will be classified according to the closest relationship. For summaries of TEAE severity, a subject will be classified according to the highest severity.

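### The planned AE summary tables split the cream arm into two periods and never count each cream subject once over the full course; adding one column would supply that figure.

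*Protocol*

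**What the plan says.** Protocol 2.2 explains that the ointment is approved for up to 4 weeks of daily use, whereas "it is the intention that MC2-01 cream will be used daily for up to 8 weeks". Protocol 8.8 accordingly wants AE frequencies "presented for the two periods, Weeks 1 to 4 and Weeks 5 to 8, separately", and adds: "Adverse events will be presented in data listings and summarized by frequency and severity for each treatment group for each period". Protocol 8.8.3 then says: "Treatment-emergent adverse events will be summarized by the overall incidence of at least one event", followed by incidence by body system and by preferred term. It gives the counting rule "Each subject will contribute only once (e.g., the first occurrence) to each of the rates" and names no time span.

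SAP 10.8.2.3 carries the split through: "An overall summary of AEs will be presented by treatment and by period (MC2-01 group only". The incidence tables by preferred term, maximum severity and maximum relationship are specified in the same way. The shells for Tables 14.3.1.1 to 14.3.1.4 have identical columns: cream Weeks 1-4, ointment Weeks 1-4 and cream Post Week 4. The list of outputs in SAP section 14 contains no other AE summary table.

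Two other SAP outputs bear on the point. The exposure table, 14.1.3, does give the cream arm a cumulative Day 1 to Week 8 column. Listing 16.2.7.1 shows every AE by subject with its period, onset and end dates, severity and relationship.

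**The concern.** The split at Week 4 is right for comparing cream with ointment over equal time. It leaves a gap for the cream alone. A product intended for up to 8 weeks of use is naturally described by the share of subjects with any event, any related event and each preferred term over the whole course. A cream subject with events before and after Week 4 appears in both cream columns, and the tables do not say how many such subjects there are. The Weeks 1-4 column can only equal or understate the full-course share. The sum of the two columns can only equal or overstate it. Severity and relationship have the same gap, because the highest grade and closest relationship are shown within each period and not over the course.

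**Working it through.** The documents state no figure here, so there is none to reproduce. The question is whether the planned columns determine the full-course proportion.

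**Inputs**
- Protocol synopsis: "It is planned to enrol approximately 60 subjects", "randomly assigned in a 1:1 ratio to receive the MC2-01 cream or the comparator". This gives 60 / 2 = about 30 on cream.
- AE rates: none are given in either document. The counts below are assumptions, shown over a range.

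**Formula.** Let *a* be the number of cream subjects with an event in Weeks 1-4, *b* the number with one after Week 4, *c* the number with events in both, and *N* the number on cream. The full-course count is *a* + *b* − *c*. The planned tables show *a* and *b* but not *c*, so the full-course count is known only to lie between max(*a*, *b*) and min(*N*, *a* + *b*).

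**Results for assumed counts**

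| N | a | b | Lowest | Highest | If periods were independent |
|---|---|---|---|---|---|
| 30 | 3 | 3 | 3/30 = 10.0% | 6/30 = 20.0% | 19.0% |
| 30 | 6 | 6 | 6/30 = 20.0% | 12/30 = 40.0% | 36.0% |
| 30 | 9 | 6 | 9/30 = 30.0% | 15/30 = 50.0% | 44.0% |
| 30 | 12 | 9 | 12/30 = 40.0% | 21/30 = 70.0% | 58.0% |
| 25 | 9 | 6 | 9/25 = 36.0% | 15/25 = 60.0% | 51.4% |

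The last column is 1 − (1 − *a*/*N*)(1 − *b*/*N*); for 9 and 6 of 30 it is 1 − 0.70 × 0.80 = 0.44. Nothing in the plan supports independence, so it only marks a point inside the range.

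**Severity rows.** Suppose one subject has a mild event in Weeks 1-4 and a severe one later, and another has the reverse. Each cream column then shows one mild and one severe subject. Over the full course there are two severe and no mild subjects. For grades below the highest, the full-course count can therefore fall below both columns, and even the lower bound above fails.

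**Does Post Week 4 complete the 8 weeks?** No. SAP 10.8.2.3 defines it as Day 29 and after, with no end, so it can include events during follow-up after Week 8.

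**Is the boundary consistent?** No. The SAP text cuts between Day 28 and Day 29, while the footnotes to shell 14.3.1.2 cut at the Week 4 visit. Protocol Table 7-2 puts that visit at Day 28 ± 2, counting Visit 1 as Day 0. SAP 9.2 counts the same visit as Day 1. On the SAP's numbering the Week 4 visit is therefore due on Day 28 + 1 = 29, with a window of Days 27 to 31. An event starting on the day of an on-schedule Week 4 visit is Post Week 4 under the text and Weeks 1-4 under the shell.

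**Denominator.** The Post Week 4 denominator is not defined. Six affected subjects are 6/30 = 20.0% of all cream subjects, but 6/25 = 24.0% if, say, 25 were still followed.

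**The case against.** The plan does what Protocol 8.8 asks, and AEs are not the primary safety endpoints. Those are HPA suppression and calcium metabolism, which are reported at both Week 4 and Week 8. The trial is a small maximal-use PK study. The width of each range cannot exceed the smaller of the two counts, so sparse rows such as single preferred terms carry little ambiguity. All of this stands and limits the weight of the point.

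Three stronger readings are tempting, and the documents do not support them.

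- *The full-course incidence is lost.* It is not. Listing 16.2.7.1 holds what is needed to count it by hand for about 30 subjects, and serious AEs and AEs leading to discontinuation have their own listings. What is missing is a planned summary table; a hand count would have to be repeated for every row.
- *The SAP breaks a promise in Protocol 8.8.3.* That sentence opens a list that continues with body system and preferred term, so its overall incidence most naturally means across body systems. The row for subjects with any TEAE in Tables 14.3.1.2 to 14.3.1.4 meets that reading within each period. The section names no full-course span, so no clear contradiction is shown.
- *A full-course column would give the incidence under 8 weeks of continuous treatment.* It would not. Protocol 6.4 lets cleared subjects stop after Week 4 at the investigator's discretion, and Protocol 7.9.2 has subjects with HPA suppression at Week 4 stop the cream but stay in the trial. The column would describe the randomised cream course, including time off treatment.

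**Conclusion.** The point holds as a gap in the summary tables. No planned AE table counts a cream subject once over the full course, and the two period columns bound that proportion without fixing it. Under the assumed 9 and 6 of 30 the gap is 20 percentage points (30% to 50%). Over the assumed pairs at *N* = 30 it runs from 10 points (3 and 3) to 30 points (12 and 9). These sizes rest on assumed counts and about 30 cream subjects; that the columns do not determine the figure rests on neither. The primary PK comparison, the HPA and calcium analyses and the Week 4 AE comparison with ointment are unaffected. This is a worthwhile reporting improvement at almost no cost. It is not evidence of missing data or of a departure from the protocol.

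**What to change.** 1. Add one cream column, Day 1 to end of study, to Tables 14.3.1.1 to 14.3.1.4 and state it in SAP 10.8.2.3. Count each subject once per row, at the highest severity and closest relationship over that span, with cream subjects in the Safety population as denominator. The subjects with any TEAE in this column are then exactly those in either period column.
2. If a column ending at the Week 8 visit is preferred, show later-onset events separately. Otherwise it will not reconcile with the open-ended Post Week 4 column.
3. Use one period boundary in the SAP text and the shell footnotes, either a fixed study day or the Week 4 visit date. State the denominator of each column.
4. Keep the Weeks 1-4 columns for the comparison with ointment. Align the output list, which titles Tables 14.3.1.2 to 14.3.1.4 as Weeks 1-4 only, with the shells.
5. Add a footnote that some cream subjects may have stopped treatment after Week 4 while remaining in the trial.

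The cost is one column in four tables, a sentence or two in the SAP and some footnotes. All the data are already collected.
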